1. BACKGROUND AND RATIONALE

Our study focus is to identify patients that have been on the ventilator for more than 72 hours receiving fentanyl infusions or its equivalents and enroll them into our study, start them on oral Methadone in order to wean off Fentanyl. Patients on mechanical ventilation are often administered opioids and other sedative medications to control pain, maintain comfort and optimize ventilatory support. The use of effective strategies to help wean patients from continuous infusions of opioids in an ICU setting that do not predispose them to continuous pain or risk of drug withdrawal has been proposed but attaining the above objective remains challenging.

Based on nomenclature used following 2002 American College of Critical Care Medicine sedation consensus guidelines, 72 hours or more on sedation was considered prolonged ICU sedation. ^[1] There has been very few randomized controlled trials on the best strategy to wean patients from prolonged infusion of opioids beyond 72 hours and there is no national consensus as regards the best strategy. Only a few studies with very small sample sizes have been used to guide current management. ^[2] During COVID-19 pandemic surge periods Massachusetts General Hospital published strategies for weaning analgesia using oral methadone which most of our ICU physicians are currently using. We do not have evidence of the benefit of this strategy and believe designing a study to assess the benefits will be useful for its continuoususe.

1.1. General Introduction

Methadone is an opioid which binds to opioid receptors to produce analgesia and sedation. It is currently in use for treating opioid dependence as well as analgesic for chronic moderate to severe pain

1.2. Rationale and justification for the Study

Variation in sedation practice may lead to undersedation or over sedation. Over sedation is associated with adverse clinical outcomes such as prolonged stay on the ventilator, prolonged ICU length of stay, delirium and increased mortality. [3]

We hypothesize that patients who get oral methadone to help wean off opioids will have shorter ICU length of stay, shorter duration on the ventilator and potentially improved hospital mortality. We hypothesize that we will increase the proportion of patients extubated by day 5.

The use of long-acting opioids by enteral administration to wean mechanically ventilated patients from sedation and analgesia has been well documented by Wanzuita et al. They used 10mg of methadone every six hours enterally while reducing the rate of fentanyl infusion by 20%.

#UTHealth Houston

a. Rationale for the Study Purpose

Based on nomenclature used following 2002 American College of Critical Care Medicine sedation consensus guidelines, 72 hours or more on sedation was considered prolonged ICU sedation. ^[1] There has been very few randomized controlled trials on the best strategy to wean patients from prolonged infusion of opioids beyond 72 hours and there is no national consensus as regards the best strategy. Only a few studies with very small sample sizes have been used to guide current management. ^[2] A randomized control trial carried out in Brazil introduced the use of Methadone after patients were on ICU sedation for 5 days, compared to Society guidelines, which was two days longer. ^[4] Current protocols recommend tapering Fentanyl based on a nursing protocolized sedation in which the dose is reduced by 25mcg per hour to bring the patient to a desired RASS (Richmond Agitation Sedation Scale score) set by the physician.

In our study, we seek to identify patients on IMV for over 72 hours and randomize them to those who will receive methadone and those that will get usual care not receiving methadone. We plan to compare any differences in ICU outcomes.

Prior randomized trials introduced the use of methadone after 5 days of ICU sedation which was much longer than the ACCM definition of 3 days on prolonged mechanical ventilation.

b. Rationale for Doses Selected

Patients will be randomized to either Oral Methadone tablets the interventional group or Control group that will receive usual care with IV Fentanyl or hydromorphone per hospital protocols. Patients on the methadone group will be started on Methadone 5mg, 10mg or 15mg every 8 hours via a feeding tube depending on Fentanyl drip rate (0-100mcg/hr, 100-200mcg/hr or >200mcg/hr) or hydromorphone drip rate (0-1.5mg/hr, 1.5-3mg/hr, or >3mg/hr), Appendix3. The rate of Fentanyl or hydromorphone will be reduced by 25% initially to bring patient to a desired RASS (Richmond Agitation Sedation Scale score) as requested by the physician. While the control group will Not get any medication and will be weaned off opioids as per usual care.

c. Rationale for Study Population

In order to test our hypothesis our population of target needed to be patients admitted to the ICU who have been on mechanical ventilation for more the 72 hours on sedation with opioids. This gives us the opportunity to be able to compare outcomes between those that will receive methadone to those that will not

d. Rationale for Study Design

A randomized control trial gives us the best tool devoid of selection bias as well as controlling for potential confounders.

#UTHealth Houston

2. HYPOTHESIS AND OBJECTIVES

2.1. Hypothesis

The study hypothesizes that patients who get oral methadone to help wean off opioids will have shorter ICU length of stay, shorter duration on the ventilator and potentially improved hospital mortality. The study hypothesizes that, there will be increase in the proportion of patients extubated by day 5.

2.2. Primary Objectives

To determine the effect of methadone on the duration on mechanical ventilation in critically ill patients receiving more than 72 hours of MV by comparing the number of ventilator free days form enrolment to the time of discharge

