2.3. Secondary Objectives

To assess the safety of methadone administration in critically ill patients while in the hospital.

To determine hospital length of stay from the time of enrollment to the time of discharge

2.4. Potential Risks and Benefits:

a. End Points – Efficacy

The study might show the efficacy and potency of methadone in decreasing the length of stay in ICU and duration of mechanically intubation in critically ill patients.

b. End Points - Safety

Adverse events that could be anticipated during the study include signs of opioid withdrawal, elevated liver enzymes, ileus, hypotension and QTC prolongation. Adverse events will be reported in the adverse events registry.

The only two adult studies reported on the use of methadone to wean opioids on mechanical ventilation showed that the much-anticipated risk of QTC prolongation was similar in both patients who received methadone and those that did not receive methadone as shown in the study by Wanzuita et al and Al-Qadheeb et al. [5] Methadone was well tolerated in both studies.

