2.5 Outcomes

a. Primary

Proportion of patients on methadone that get extubated by day number 5 from the date of intubation

b. Secondary

Proportion of patients that develop prolonged QTC after administration of methadone. Others will be ICU length of stay, ICU mortality, hospital length of stay and hospital mortality.

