3.3. Inclusion Criteria

Patients will be enrolled only if they consented and they meet all of the inclusion criteria listed below.

- 1. Patients 18 years or older
- 2. Patients on IMV for more than 72 hours
- 3. Patients infused Fentanyl or Hydromorphone for more than 72 hours
- 4. Patients with evidence of reversal of process that caused respiratory failure, adequate oxygenation (PaO2/FIO2>200; Positive end expiratory pressure (PEEP)≤8 and Ph≥7.2
- 5. Patients hemodynamically stable
- 6. Patients with a failed single or multiple attempts at spontaneous breathing trials

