6. METHODS AND ASSESSMENTS

Based on the assumptions of successful extubation by day 5 of 50% of patients in the methadone group and 20% of patients in the control group and using a two tailed alpha level of 5%, a power of 80% our sample size calculation comparing proportions of two groups yielded 76. A 5% fallout as correction factor was 4 leaving us with a sample size of 80 patients. Statistical methods will include descriptive statistics and time to event analysis. Baseline characteristics will be reported. Data will be collected on a data collection sheet prior to transfer to REDCAPs database (Appendix 6). We will generate Kaplan-Meier curves and for comparison of hazard between groups we will use Cox regression (Cox proportional hazards model). Patients who die will be censored at time of death. Time of weaning will take into consideration only patients who were permanently disconnected from the ventilator. QTc values will be obtained from patient monitors and documented on data collection tool daily.

Randomization tables will be generated using REDCAPs database by study statistician. At the end of the study recorded information from REDCAPs will be exported to STATA for statistical analysis.

#UTHealth Houston

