10. SAMPLE SIZE AND STATISTICAL METHODS

10.1. Determination of Sample Size

Based on the assumptions of successful extubation by day 5 of 50% of patients in the methadone group and 20% of patients in the Non Methadone group and using a two tailed alpha level of 5%, a power of 80% our sample size calculation comparing proportions of two groups yielded 76. A 5% fall out as correction factor was 4 leaving us with a sample size of 80 patients.

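### The primary objective is measured by ventilator-free days to discharge, not by the powered day-5 extubation outcome, and that count depends on length of stay

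*Combined protocol and SAP*

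**What the plan says.** Section 2.2 sets the primary objective as the effect of methadone on duration of mechanical ventilation, to be determined "by comparing the number of ventilator free days form enrolment to the time of discharge". It does not say whether ICU or hospital discharge is meant, and it gives no value for patients who die.

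Section 2.5 names another measure as primary: "Proportion of patients on methadone that get extubated by day number 5 from the date of intubation". The secondary outcomes there are QTc prolongation, ICU and hospital stay, and ICU and hospital mortality. Ventilator-free days are not among them.

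The sample size in sections 6 and 10.1 assumes day-5 extubation rates of 50% on methadone and 20% on control. Section 10.1 describes the calculation in these words: "using a two tailed alpha level of 5%, a power of 80% our sample size calculation comparing proportions of two groups yielded 76". Section 6 also plans Kaplan-Meier estimates and a Cox model: "for comparison of hazard between groups we will use Cox regression (Cox proportional hazards model". Section 10.2 assigns chi-square tests to categorical variables and t-tests to continuous ones.

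Two further statements matter. The hypothesis in section 2.1 is that methadone patients "will have shorter ICU length of stay, shorter duration on the ventilator and potentially improved hospital mortality". Section 2.3 uses the window of 2.2 for another purpose: "To determine hospital length of stay from the time of enrollment to the time of discharge".

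**The concern.** There are two linked problems.

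First, the plan gives two answers to the question of which result decides the primary objective. Section 2.2 points to a count of days. Sections 2.5, 6 and 10.1 point to a proportion at day 5. Both stand in the current text, so the objective could be declared met or missed on either.

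Second, the count in 2.2 does not isolate ventilation. Its window closes at discharge, and treatment may itself move discharge. A patient who leaves sooner has fewer days in which to be ventilator-free. Randomisation removes baseline confounding, but it does not undo this coupling with stay, which is built into the definition.

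The same shortening of ventilation can therefore read as a gain, as nothing or as a loss, depending on what happens to stay.

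**Working it through.** **1. Which measure the sample size belongs to.** Inputs from 10.1: 50% against 20%, two-sided alpha 5%, power 80%. Section 4.1 gives 1:1 allocation.

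- Arcsine formula: h = 2·arcsin(√0.5) − 2·arcsin(√0.2) = 0.6435; n = 2(1.960 + 0.842)²/h² = 37.9, so 38 per arm and 76 in total.
- The pooled-variance formula gives 38.5, so 39 per arm and 78 in total, within two patients of the plan.
- Dropout: 76/0.95 = 80.

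The plan's 76 and 80 are reproduced, and they belong to the binary day-5 outcome. For ventilator-free days the documents give no mean, SD or target difference. By normal approximation, 38 per arm has 80% power for a difference of (1.960 + 0.842)·√(2/38) = 0.64 SD. That is 3.2 to 6.4 days for an assumed SD of 5 to 10 days.

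**2. What the 2.2 count measures.** For a survivor extubated once:

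(discharge − enrolment) − (extubation − enrolment) = discharge − extubation.

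This is the post-extubation stay, whether discharge is from the ICU or the hospital. The difference between arms is therefore the change in total stay minus the change in ventilator days. With ventilation 3 days shorter on methadone:

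| Change in total stay (days) | Arm difference on the 2.2 measure (days) |
|---|---|
| 0 | 0 − (−3) = +3 |
| −1 | −1 − (−3) = +2 |
| −3 | −3 − (−3) = 0 |
| −5 | −5 − (−3) = −2 |

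No assumption about distributions is needed. The identity does not cover deaths, reintubations or patients discharged while still ventilated.

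**3. Illustration at the plan's own effect size.** Section 3.3 requires "Patients on IMV for more than 72 hours", so day 5 from intubation falls about 2 days after the earliest enrolment. Ventilator time after enrolment was calibrated to 20% and 50% extubated by 2 days, with 38 analysed per arm. Assumed, not in the documents: no deaths, a mean control post-extubation stay of 8 days, and gamma-distributed times with shape 1, 2 or 4.

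Mean ventilator days after enrolment are then 9.0, 4.9 and 3.5 on control and 2.9, 2.4 and 2.2 on methadone, a benefit D of 6.1, 2.5 and 1.3 days. The chi-square test on day-5 extubation is significant in 80% of simulated trials. The section 10.2 t-test, applied to the 2.2 measure, gives:

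| Total stay on methadone | Mean difference (days; shape 1/2/4) | Significant result (shape 1/2/4) |
|---|---|---|
| Unchanged | +6.1 / +2.5 / +1.3 | favours methadone in 66% / 36% / 25% |
| Shorter by D | 0 | about 2.5% each way |
| Shorter by D + 2 days | −2.0 | favours control in 22% / 41% / 69% |

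The ventilation benefit is identical in all three rows; only stay changes.

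**4. Deaths.** Assume that survivors are alike in both arms (8 ventilator and 8 recovery days) and that mortality is 15% against 25%, with half of deaths on the ventilator and the rest spread evenly over recovery. The 2.2 difference is then +0.6 days if days are counted to death, +0.8 if death scores 0, and 0 if deaths are excluded. Section 2.2 does not choose among these.

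**The case against.** The strongest reply is that the governing endpoint is already clear. Day-5 extubation is in the hypothesis, is labelled primary in 2.5 and is the only powered outcome. The chi-square rule in 10.2 fits it, and no analysis text mentions ventilator-free days. On this view 2.2 is a loose sentence to be tidied. It is true that the day-5 outcome and the Cox model still address ventilation and that the sample size is sound. But 2.2 is the one place that says how the primary objective is to be determined, and nothing in the plan overrides it.

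The simulated percentages also rest heavily on assumptions. Pairing the t-test with this count applies a general rule in 10.2; the plan does not make the pairing itself. With 1 day instead of 2 between enrolment and day 5, the figures for unchanged stay fall from 66%, 36% and 25% to about 26%, 13% and 10%. Reversal requires stay to fall by more than ventilator time, which the protocol does not predict; it expects only that both shorten. These points stand. The percentages show dependence on stay and do not rank the endpoints. The case rests on the identity.

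Finally, the day-5 outcome has a difficulty of its own. Sections 3.3 and 3.4 allow enrolment after day 5 from intubation, and such a patient cannot meet it. If 10% or 25% of patients were in that position (assumed), power at 38 per arm would fall from 80% to about 74% or 62%. That is a separate defect of the existing primary outcome. Aligning 2.2 neither creates nor worsens it, but does not cure it either.

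**Conclusion.** The concern holds and must be fixed. The measure in 2.2 differs from the labelled and powered primary outcome and has no power basis. For survivors extubated once it reduces exactly to post-extubation stay. It gives the true change in ventilator days only if total stay is unchanged, shows no difference if stay falls by the same number of days, and favours control if stay falls by more: +3, 0 and −2 days for a 3-day ventilation gain with stay shorter by 0, 3 and 5 days. That result follows from the definition alone. The simulated percentages depend on the assumptions listed with them. The sample size of 76 (80 with dropout) is not in question.

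**What to change.** Reword 2.2 so that the primary objective is assessed by the powered outcome: the proportion extubated by day 5, compared between arms in all randomised patients. Add one line naming the Kaplan-Meier and Cox analysis of section 6 as supportive. The sample size is unchanged and no new patients or data are needed. The day-5 clock in 2.5 is not altered by this change and needs separate attention.

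If the team wishes to keep ventilator-free days, list them as secondary in 2.5. Count them over a fixed window from randomisation, for example the 30-day participation limit already in 4.2. State the value given to death, and report mortality beside them. Section 4.2 already collects ICU and hospital stay and mortality. The added cost is that reintubation and status after discharge must be taken from the chart to the end of the window, or an assumption stated.

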2.3. Secondary Objectives

To assess the safety of methadone administration in critically ill patients while in the hospital.

To determine hospital length of stay from the time of enrollment to the time of discharge

2.4. Potential Risks and Benefits:

a. End Points – Efficacy

The study might show the efficacy and potency of methadone in decreasing the length of stay in ICU and duration of mechanically intubation in critically ill patients.

b. End Points - Safety

Adverse events that could be anticipated during the study include signs of opioid withdrawal, elevated liver enzymes, ileus, hypotension and QTC prolongation. Adverse events will be reported in the adverse events registry.

The only two adult studies reported on the use of methadone to wean opioids on mechanical ventilation showed that the much-anticipated risk of QTC prolongation was similar in both patients who received methadone and those that did not receive methadone as shown in the study by Wanzuita et al and Al-Qadheeb et al. [5] Methadone was well tolerated in both studies.

2.5 Outcomes

a. Primary

Proportion of patients on methadone that get extubated by day number 5 from the date of intubation

b. Secondary

Proportion of patients that develop prolonged QTC after administration of methadone. Others will be ICU length of stay, ICU mortality, hospital length of stay and hospital mortality.

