3.4. Exclusion Criteria

All subjects meeting any of the exclusion criteria at baseline will be excluded from participation.

- 1. Patients with history of opioid drug abuse
- 2. Patients receiving schedule II narcotics on a chronic basis for longer than 6 months prior to ICU admission or on other analgesic infusions other than Fentanyl or Hydromorphone
- 3. Patients with cervical spinal cord injury or neuromuscular disease
- 4. Patients with end stage liver disease at ICU admission (ie, International normalized ratio ≥2and not taking warfarin and/or a total serum bilirubin ≥1.5 times above normal limits
- 5. Patients with prolonged QTc interval ≥500
- 6. Patients with prior history of cardiac conduction defects or suddendeath
- 7. Patients with QTc increase of ≥60 milliseconds above the value of prior EKGs measured during current ICU admission
- 8. Patients with more than 5 days on IV analgesia
- 9. Patients intubated for more than 30 days
- 10. Patients without feeding tubes
- 11. Patients not receiving enteral feeding
- 12. Exclusion of patients in a comatose state
- 13. Exclusion of patients in Status Epilepticus
- 14. Exclusion of post-operative patients

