5. STUDY DESIGN

5.1. Summary of Study Design

The study is randomized clinical trial. The duration of the study is 2 years. Patients will be screened to confirm they meet study criteria. Consent will be obtained from the legal authorized representative. Initial demographic data will be obtained using REDCap Database. Patients will be randomized to either Oral Methadone tablets or Non-Methadone group. The control group will receive usual care with IV Fentanyl or hydromorphone per hospital protocols as on appendix 1. Patients on the methadone group will be started on Methadone 5mg, 10mg or 15mg every 8 hours depending on Fentanyl drip rate (0-100mcg/hr, 100-200mcg/hr or >200mcg/hr) or hydromorphone drip rate (0-1.5mg/hr, 1.5-3mg/hr, or >3mg/hr). The rate of Fentanyl or hydromorphone will be reduced by 25% initially. If patients require additional sedation later, this will be administered per usual care and the total amount of additional opioids will be documented and used for analysis as morphine milligram equivalents (MME). Likewise, patients could be weaned more than 25% if they showed signs of tolerance to lesser sedation.

At Subsequent encounters: Rate of Fentanyl or Hydromorphone drip will be reduced by 25% every 24 hours until the patient is extubated from the ventilator.

Continuous IV opioids for analgesia for patients on mechanical ventilation is routine clinical care and will not be denied to patients. Once patients are extubated oral methadone will be discontinued and patient monitored for any opioid withdrawal symptoms and treated per protocol as shown on appendix 2 based on their clinical opiate withdrawal scale (COWS) appendix 4. For those with a score of less than 25 oral methadone will no longer be required. For those with a COWS score of >25 methadone will be resumed for a short taper of 3 days. The above can be illustrated as on study protocol flow on Appendix 5 and details on methadone taper as on Appendix 2.

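### The day-5 primary outcome is timed from intubation, but patients can enter only after more than 72 hours of ventilation, so treatment has under 48 hours to act (at most 72 by calendar days), and late entrants have none

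*Combined protocol and SAP*

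**What the plan says.** Section 2.5 defines the primary outcome as the "Proportion of patients on methadone that get extubated by day number 5 from the date of intubation". The clock starts at intubation, and the wording names only the methadone patients.

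Section 3.3 sets two time thresholds for entry: "Patients on IMV for more than 72 hours" and "Patients infused Fentanyl or Hydromorphone for more than 72 hours". It also requires at least one failed spontaneous breathing trial.

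Section 3.4 sets two upper limits by excluding "Patients with more than 5 days on IV analgesia" and "Patients intubated for more than 30 days".

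Section 2.2 states the primary objective differently, as "comparing the number of ventilator free days form enrolment to the time of discharge". The hypothesis in section 2.1 says "there will be increase in the proportion of patients extubated by day 5" and gives no starting point for day 5. Section 1.2 and the sample size text in sections 6 and 10.1 are equally silent on the origin.

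Under section 5.1 the methadone arm has an initial 25% cut in the infusion, after which the "Rate of Fentanyl or Hydromorphone drip will be reduced by 25% every 24 hours until the patient is extubated from the ventilator". The same section allows faster weaning when tolerated.

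**The concern.** Much of the outcome period has passed before a patient can be randomised. By entry, at least 72 of the 120 hours have gone by with both arms under the same care and nobody extubated. Only the remainder can show a treatment effect, and that remainder shrinks with each hour of delay in screening, consent or meeting the stability criteria.

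The exclusions do not close the gap. The 5-day limit on IV analgesia keeps most entries near days 3 to 5 if the infusion began at intubation. A patient intubated for 6 to 30 days whose infusion started later is still eligible. That patient passed day 5 before randomisation and can only be counted as a failure.

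Randomisation balances entry time between arms in expectation, so the main harm is dilution and lost power, not bias. The second harm is ambiguity. The primary objective and primary outcome differ in both measure and time origin, so two analysts could report different primary results from the same data. The primary comparison and the sample size both rest on this proportion.

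**Working it through.** **Inputs.** Outcome limit: day 5 from intubation (2.5). Minimum ventilation at entry: more than 72 h (3.3). Rates 50% and 20%, two-sided alpha 5%, power 80%, total 76, raised to 80 for 5% dropout (6 and 10.1). Allocation 1:1 (4.1), so 38 per arm.

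**1. The plan's own sample size reproduces.**
- Pooled-variance formula: n per arm = [1.96 × √(2 × 0.35 × 0.65) + 0.8416 × √(0.25 + 0.16)]² / 0.30² = 38.48, rounded up to 39, total 78.
- Arcsine formula: 37.9, rounded up to 38, total 76 exactly.
- Dropout: 76 / 0.95 = 80.

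The arithmetic is sound. The open question is what the two rates measure.

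**2. Window left for the earliest entrant.**
- Elapsed time: 5 × 24 − 72 = 48 h. Entry needs more than 72 h, so the window is strictly under 48 h.
- Calendar days, intubation date as day 0: at most 48 to 72 h to the end of day 5, depending on the clock time of intubation. The 72 h applies only to intubation at the very start of that date.
- Calendar days, intubation date as day 1: at most 24 to 48 h.
- Entry after day 5: none.

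**3. What this does to power.** The documents give no entry-time distribution, so these are illustrations. Power is exact for the chi-square test without continuity correction, 38 per arm, two-sided 5%.

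*(a) A share f enters after day 5 and cannot succeed; the rest keep 50% and 20%.* The rates become 0.5(1 − f) and 0.2(1 − f).

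| f | Rates | Power |
|---|---|---|
| 0 | 50% vs 20% | 80.0% |
| 5% | 47.5% vs 19% | 77.0% |
| 10% | 45% vs 18% | 73.8% |
| 20% | 40% vs 16% | 66.5% |
| 30% | 35% vs 14% | 58.2% |

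A normal approximation gives slightly lower values: 79.5%, 72.6%, 64.9% and 56.9% at f = 0, 10%, 20% and 30%.

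*(b) The rates describe 5 days after enrolment, with constant hazard, but only t days are available.* The rates become 1 − 0.5^(t/5) and 1 − 0.8^(t/5).

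| t | Rates | Power | n per arm for 80% (pooled formula) |
|---|---|---|---|
| 5 days | 50% vs 20% | 80.0% | 39 |
| 3 days | 34.0% vs 12.5% | 61.8% | 60 |
| 2 days | 24.2% vs 8.5% | 47.2% | 87 |
| 1 day | 12.9% vs 4.4% | 28.7% | not calculated |

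*(c) The rates already describe the intubation clock.* Power stays at 80%. The full 30-point difference must then arise in under 48 h, or at most 72 h.

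**4. The window against the weaning schedule.** On the default schedule in section 5.1, only the initial cut and the 24 h cut fall before 48 h. The infusion is then at 0.75² = 56% of its starting rate if cuts compound, or 1 − 2 × 0.25 = 50% if they are linear.

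**The case against.** The only definition of day 5 is the one in section 2.5, so the hypothesis and sample size text most naturally inherit the intubation clock. The enrolment clock in section 2.2 belongs to ventilator-free days, not to day 5. On that reading scenario (c) applies and no nominal power is lost. This is a fair point. The losses in scenario (b) are conditional on another reading and on constant hazard, and they should not be quoted as the expected loss. Scenario (c) still leaves a 30-point effect to be produced in under two days, and the plan does not justify the rates for that window.

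The share entering after day 5 may be small, since it requires an infusion that began well after intubation. Nothing in the documents points to 20% or 30%; at 5% power is 77%. This too is fair, but entries on days 4 and 5, which the criteria plainly allow, also have little or no window.

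The infusion argument is only supportive. Section 5.1 foresees extubation on a running infusion and permits faster cuts. Appendix 2, to which section 7.1 refers for dosing, describes a 25% reduction with each replacement dose, a different pace. Those passages need reconciling, and the 56% and 50% figures hold only for section 5.1 as written.

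Two smaller points. At 40 per arm, the full planned number, the 80%, 62% and 47% become 82%, 64% and 49%. The Kaplan-Meier and Cox analyses in section 6 do use the time data, but the sample size does not rest on them.

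**Conclusion.** The concern holds, and the plan must be corrected. As written, no participant can have more than 48 hours of post-randomisation time counting towards the primary outcome (72 hours on the most generous calendar count). Those enrolled after day 5 have none and add only failures to both arms. That follows from sections 2.5, 3.3 and 3.4 without any assumption.

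The size of the power loss does depend on assumptions. It ranges from none, if the 50% and 20% were chosen for the intubation clock and nobody enters after day 5, to a fall to about 47% if they describe five days from enrolment and two are available. The documents do not say which applies. Separately, the primary objective and primary outcome disagree in measure as well as in origin, and nothing in the plan resolves this.

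**What to change.** Define the primary outcome in section 2.5 as the proportion of all randomised patients, compared by arm, who are successfully extubated within 120 hours after randomisation. Carry the same definition into sections 6 and 10.1, and align the hypothesis (1.2 and 2.1) and the primary objective (2.2) with it. If the sponsor prefers ventilator-free days from enrolment as the primary measure, the outcome and sample size must be rewritten around that instead; one measure and one origin should appear throughout.

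State which clock the 50% and 20% rates came from and re-justify them for the chosen one. Confirm that extubation date and time is recorded. The Appendix 6 form, as far as it can be read, shows ventilator hours at randomisation but no extubation time; the table may be incomplete.

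The cost is wording in six places, possibly one data field, and a fresh justification of the two rates, which could change the sample size. No dose or clinical rule is affected. The change should be settled before any outcome data are examined, including the interim analysis at 40 patients (10.2).
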